### **4.2.2. Device choice**

Traditionally, full blood counts (FBCs) have been analysed using large laboratory-based high throughput microplate or tube equipment such as the Horiba Pentra with an average vein to report time of 4 hours [8]. Recently the haematology point of care test (POCT) market has grown and a number of discipline-specific novel devices have been developed to analyse FBCs. Several analysers capable of 3-part differentials (neutrophils, eosinophils, and basophils grouped together to produce a total granulocyte count) are currently commercially available including POCH-100i (Sysmex Corporation, Kobe, Japan) and the ABX Micros series (Horiba Medical, Northampton, UK) OLO (Sight Diagnostics).

Neutrophil count is an important criterion to clinicians when making decisions about treatment of oncology patients. The availability of POCT analysers capable of producing an FBC with a 5-part differential (including neutrophils, lymphocytes, monocytes, eosinophils and basophils) is limited but includes the HemoScreen (PixCell Medical, Israel), the Yumizen H500 (Horiba Medical, Northampton, UK), and the OLO (Sight Diagnostics) System equipment

The Yumizen H500 is based on Horiba's Micros platform, is aimed at the point-of-care and primary care market, and has comparable accuracy to the Horiba Pentra 120 series [9]. The device can provide a result within 2 minutes and has both open and closed venous tube options, making it suitable for paediatric and capillary samples. The device has been evaluated for the improvement of point of care testing for paediatric patient groups and been found to have exceptional correlation with the Horiba Pentra DX120 by the Cardiff & Vale Health Board with an improved vein to report time of less than 15 minutes [10].

The OLO white cell differentiation kit also undertakes a 5 part white cell differentiation and also includes platelet count, the kit is in commercial use and will be evaluated locally through the work packages in this study. The technology uses an AI based camera based technology.

We are collaborating with Sight Diagnostics who are distributor and manufacturer of the OLO System. The equipment is CE marked for clinical use and has undergone testing to demonstrate that it can effectively report on a patients' total WBC count and five-part WBC differential count and platelet count ..

Compared to the Yumizen and Horiba systems the OLO kit is portable with a small footprint and weight costs less, and can be used with both venous blood samples and samples taken using the novel Microcuvette finger prick blood sample device. However, it has a lower throughput and longer time to result (11 minutes minimum). Despite these drawbacks, the system is potentially better suited than its 5-part differential competitors to niche remote locations in which a patient with suspected neutropenic sepsis may present, for example the inpatient hospital assessment unit, GP practice, and Tenovus chemotherapy bus.

The Sight OLO System has been evaluated against a variety of comparator systems in the public and private hospital sector, main and oncology lab environment, and adult and children hospital settings with comparable results [10-15].

.

Patient centred values have been a key area of work within NHS Wales and include the desire for patients to have greater control over their treatment. We believe the OLOLO (Sight Diagnostics) system has the potential to offer this control. However, there remains a lot to do in this arena with respect to effective use, location of use (for example clinic, Tenovus bus, patient home), operator, and patient acceptance. Assessment is required in important sub-populations including the less technologically aware, less dextrous and frailer individuals.

## **5 Trial objectives/endpoints and outcome measures**

The proposal aims to investigate the most effective placement of the OLO (Sight Diagnostics) system. Dependent upon this evaluation it will lead to the submission of a funding request for a full scale randomised controlled trial within NHS cancer services, led by Wales.

### **5.1 Objectives**

To clinically evaluate the investigational device (OLO (System) versus the comparator standard laboratory device for the management of chemotherapy-related suspected neutropenic sepsis and pre-chemotherapy borderline neutropenia.

The secondary objectives of the study are:

1. To assess the feasibility of recruiting patients and use of the OLO (System);
2. To assess the safety of the OLO (Sight Diagnostics) System in association with the UKONS Oncology/Heamatology 24 hour guidance and triage screening tool (Appendix 1) for patients who telephone for medical advice with suspected neutropenia and sepsis, to maximize both patient safety and independence;
3. To assess patient and staff acceptability for the investigative device;
4. To assess costs, including issues around hospital care/treatment and admissions.
5. To assess which chemotherapy regimens are most likely to be associated with neutropenic sepsis and what current treatment management is;
6. Through communication with key stakeholders and Welsh Government, explore the framework required to adequately inform the potential integration of the investigational device and triage questions into routine practice, within Wales and beyond;
7. To design a larger UK-wide trial, in collaboration with patient representatives, to formally assess the investigational device for routine use within the NHS.

## 5.2 Primary outcomes measure(s)

### ***Clinical evaluation of the OLO (Sight Diagnostics) system:***

- Neutrophil count from OLO (Sight Diagnostics) system and standard laboratory test full blood count (FBC).

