## **4.2 Justification for trial design and investigational and comparator device choice**

### **4.2.1 Local audit**

An audit conducted at VCC in 2017 identified that 96 cancer patients with chemotherapy-related suspected neutropenic sepsis were admitted to VCC over a period of 3 months [7]. One third had confirmed neutropenic sepsis. Two thirds did not have neutropenia, a proportion of whom may have avoided admission if this feasibility and subsequent larger trial are successful. This pool of retrospective patient data has been used to inform the design of this feasibility study.

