## 5.3 Secondary outcomes measure(s)

### ***Feasibility of recruiting patients and use of the OLO (Sight Diagnostics) system:***

- Proportion of those recruited from those consented and/or approached
- Proportion of recruited participants with a valid (as opposed to an invalid test result) from all recruited participants. A valid result is when the OLO system neutrophil result is  $\pm 0.2 \times 10^9/L$  of the laboratory gold standard result;
- Proportion of recruited participants returning the follow-up survey from all recruited participants;
- Number and type of OLO System (Sight Diagnostics) device flags and error codes raised during device operation for fingerprick versus venous blood sample to assess device accuracy;
- Number of re-takes of finger prick versus venous blood sample to assess device accuracy.
- Number of cases in which a discrepancy between the OLO System and gold standard would change the management of the patient, according to retrospective clinical review.
- Number of patients with valid OLO System test results for:
  - Haemoglobin – (validity  $\pm 0.7$  g/L)
  - Platelets – (validity  $\pm 15 \times 10^9/L$ )
  - Lymphocytes – (validity  $\pm 0.3 \times 10^9/L$ )

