During participation in the study we will collect information about the patients suspected neutropenic sepsis, antibiotic treatment, hospital discharge, and follow up from their medical records and other data systems (for example, CANISC, Chemocare, local UKONS ACCESS-based spreadsheet) held within Velindre University NHS Trust.

If the patient develops a new medical condition, or an existing condition worsens during participation in the study or at a withdrawal visit, then the healthcare professional may contact the patient and ask them about this, until it has completely resolved.

### **12.1.6 ..... Investigation device test results**

The results of the investigational device blood tests will not be shared with the participant or used to manage the treatment pathway of the patient. The treating consultant will be told the results of the study tests after the participants condition has been successfully treated so that we can find out if it would have changed how the participant was treated. We intend to use the results of this feasibility study to inform the development of a larger UK-wide randomised study in which we intend to use the results of the investigational device(s) to manage patient pathways.

### **12.1.7 ..... Review of existing neutropenic sepsis data held at site**

The VCC Service Improvement team conducts regular audits of UKONS neutropenic sepsis data to meet UK UKONS reporting requirements. The team will provide existing clinical data routinely collected from the type of patient eligible for WP1 Cohorts 1 and 2 to the CTR for analysis and review in parallel to the WP1 device cohort study data. Fully anonymised audit data will be transferred to the CTR following CTR and Sponsor data protection guidance and procedures, and analysed alongside the other WP1 and WP2-3 data by the Statistician.

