## **14 Statistical considerations**

### **14.1 Sample size**

#### **14.1.1 WP1 Device cohort study**

##### **Cohorts 1 and 2 combined:**

We will evaluate the concordance between the OLO neutrophil result and the standard of care laboratory result from the same time period, across all patients with a valid output. A valid OLO neutrophil result will be one which produces a test result which is within  $\pm 0.2 \times 10^9/L$  of the standard laboratory result.

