## **15 Analysis**

### **15.1 Quantitative analysis of WP1 device cohort evaluation**

All quantitative analysis will be documented in the SAP [36] prior to implementation of the analysis.

As this is a feasibility study, statistical analysis of study outcomes will be descriptive in nature. Continuous data will be reported as means and standard deviations, or medians and interquartile ranges, as appropriate. Categorical data will be reported as frequencies and proportions. Outcomes will be estimated with their associated 95% confidence intervals.

No formal hypothesis testing will take place.

While subsequent funding is not formally linked to satisfying any specific progression criteria, we propose the following as indicators that a larger study is feasible (NB. Failure to meet one or more of the criteria would indicate that modifications are required, with potentially further feasibility testing, prior to a larger study) as described in Table 7.

**Table 7.** Trial progression criteria

Outcome	Criteria
Recruitment	At least 80% of patients approached to take part provide consent
Intervention adherence	At least 90% of recruited participants receive the OLO test
Intervention fidelity	A valid test result is obtained from at least 90% of recruited participants who receive the OLO test
Survey fidelity	A survey is completed and returned from at least 80% of recruited participants who are given the survey
Data collection	At least 80% of recruited participants have clinical outcome data available for statistical analysis
Staff focus groups	Focus group data indicates that the OLO test is acceptable
Patient focus groups	Focus group data indicates that the OLO test is acceptable

There will be no interim analyses other than TMG review of WP1 SAE's at TMG meetings, Trial Manager review of screening logs through the WP1-3 recruitment phases, and Trial Manager review of data entry after approximately half of the participants have been recruited to WP1.

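### The primary outcome names no contrast, concordance is limited to results that already agree, and Table 7's only accuracy indicator cannot show missed neutropenia

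*Protocol*

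**What the plan says.** - **Primary objective (5.1).** To evaluate OLO against the laboratory device "for the management of chemotherapy-related suspected neutropenic sepsis and pre-chemotherapy borderline neutropenia".
- **Primary outcome (5.2; the synopsis says the same in substance).** "Neutrophil count from OLO (Sight Diagnostics) system and standard laboratory test full blood count (FBC". No difference, agreement statistic or classification is named.
- **Sample size (14.1.1, opening paragraph, which takes both device cohorts together).** The stated aim is: "We will evaluate the concordance between the OLO neutrophil result and the standard of care laboratory result from the same time period". The sentence then restricts this to patients with a valid output, and the next sentence defines a valid OLO neutrophil result as one within ±0.2 x10^9/L of the laboratory.
- **Secondary feasibility outcomes (5.3).** "Proportion of recruited participants with a valid (as opposed to an invalid test result) from all recruited participants". The definition follows: "A valid result is when the OLO system neutrophil result is" within ±0.2 x10^9/L of the laboratory. The same list has a count of discrepancies that would change management on retrospective clinical review, with no limit attached.
- **Progression indicators (15.1, Table 7).** There are seven rows: recruitment, adherence, fidelity, survey, data collection and two focus-group rows. Fidelity is the only one that touches accuracy: "A valid test result is obtained from at least 90% of recruited participants who receive the OLO test". Its denominator is those tested, whereas 5.3 uses all recruited.
- **Threshold (4.1).** Neutropenic sepsis in the UK is described as usually involving a neutrophil count ≤0.5 x10^9/L.
- **Next step (12.1.6).** In the larger randomised study, "we intend to use the results of the investigational device(s) to manage patient pathways".

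**The concern.** The intended use is to decide who is neutropenic. The costly error is then a patient who is neutropenic by the laboratory and is reported as not neutropenic. Three pieces of the protocol together can leave that error out of view.

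First, the primary outcome does not say how the two counts are to be compared. Second, the one elaboration assesses agreement among results that have already passed an agreement test, which removes every large error before the analysis starts. Third, the only accuracy indicator is a symmetric tolerance that treats a reading 0.15 too high and one 0.15 too low alike, whichever side of 0.5 they fall.

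At stake is the message carried into the larger trial. The fidelity row could be reported as met by a device that misses a sizeable share of neutropenic patients.

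**Working it through.** **Reproducing the plan's figure.** Section 14.1.1 gives 77.8% to 95.5% for 90% valid in Cohort 1. The Wilson 95% interval for 43/48 is 77.8% to 95.5%, so the plan uses Wilson intervals and they are used below. (43/48 = 89.6%, just under the 90% row.)

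**Inputs.**
- Planned recruitment is 72 in Cohorts 1 and 2, of whom 48 are in Cohort 1 (synopsis, 9.3.1). The planned 65 and 43 are valid results, not numbers tested.
- The fidelity row is at least 90% valid among those tested (Table 7).
- Neutropenic share: "One third had confirmed neutropenic sepsis" (4.2.1). Applied to Cohort 1, 48/3 = 16. This is an assumption; 12 and 20 are shown as a range. No Cohort 2 patient is assumed to be at or below 0.5.

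**Failures the row allows.** Failures = N − ceil(0.9 × N).
- All 72 tested and pooled: ceil(64.8) = 65 valid, so 7 may fail.
- Cohort 1 alone: ceil(43.2) = 44 valid, so 4 may fail.
- At the 90% adherence floor: ceil(64.8) = 65 tested, ceil(58.5) = 59 valid, so 6 may fail.

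**Sensitivity if every allowed failure is a missed neutropenia.**

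| Row applied to | Failures | 12 neutropenic | 16 neutropenic | 20 neutropenic |
|---|---|---|---|---|
| All 72 | 7 | 5/12 = 42% (19–68) | 9/16 = 56% (33–77) | 13/20 = 65% (43–82) |
| 65 tested | 6 | 6/12 = 50% (25–75) | 10/16 = 63% (39–82) | 14/20 = 70% (48–86) |
| Cohort 1, 48 | 4 | 8/12 = 67% (39–86) | 12/16 = 75% (51–90) | 16/20 = 80% (58–92) |

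Parentheses are Wilson 95% intervals in per cent. Table 7 does not say whether the row is pooled or per cohort.

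**Why these are not bounds.** A laboratory count of 0.4 read as 0.55 differs by 0.15. It is valid, yet it crosses 0.5. Any laboratory count above 0.3 and up to 0.5 can be misread in this way without failing the row.

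**A case that needs no extreme allocation.** Assume laboratory counts among neutropenic patients are uniform on 0 to 0.5, and OLO error is normal with SD 0.05.
- Shift +0.12: share valid = Φ((0.20 − 0.12)/0.05) = Φ(1.6) = 94.5%. Share missed ≈ 0.12/0.5 = 24%.
- Shift −0.12: share valid is again 94.5% by symmetry (ignoring the floor at zero). Share missed is 0% to the nearest tenth of a per cent.

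Simulation gave the same figures. The row reads identically for a device that misses a quarter of neutropenic patients and for one that misses almost none.

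**The case against.** **The SAP may settle the statistic.** Section 15.1 defers quantitative analysis to the SAP, and the choice of agreement statistic can properly sit there. That stands. But the restriction to valid results and the content of Table 7 are fixed in the protocol, and an SAP that followed them would inherit both. A reader could take a valid output to mean simply an error-free reading, but 14.1.1 defines it by closeness to the laboratory. Section 14.5, which includes data from all participants, sits awkwardly with that restriction.

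**Table 7 is not a decision rule.** A reader might infer that a secondary proportion decides the trial and the primary outcome decides nothing. The documents do not support that. Section 15.1 calls the rows indicators not formally linked to funding, section 5 makes the funding request depend on the evaluation as a whole, and section 6.4 adds an options appraisal with a safety component.

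**The error is counted elsewhere.** A reader might also infer that nobody will look at missed neutropenia. Section 5.3 counts management-changing discrepancies, and 12.1.6 has the consultant review the OLO result afterwards for that purpose. What is missing is a limit and a place among the indicators.

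**The allocation is extreme.** This is fair. If 7 failures fell at random among 72 patients, the chance that all landed in the 16 neutropenic would be C(16,7)/C(72,7) = 11,440/1,473,109,704, about 0.0008%. A fixed ±0.2 is also proportionally tighter at high counts (5% of 4.0, but 50% of 0.4), so failures may well fall mostly outside the neutropenic group. That argues against reading 56% as a forecast. It also shows that the row may say little about performance near 0.5.

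**The one third may not transfer.** The audit covered suspected neutropenic sepsis admissions generally. Cohort 1 is described as out-of-hours and excludes patients unable to consent. Hence the range above.

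**Conclusion.** The point holds in limited form. The protocol leaves the primary comparison unnamed, restricts concordance to results that already agree, and offers one accuracy indicator that is blind to the direction of error and to the ≤0.5 threshold. Missed neutropenia can go unseen in the stated indicators.

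The illustrative sensitivities compatible with the row are 56% pooled and 75% within Cohort 1, given about 16 neutropenic patients and all allowed failures being misses. They are neither forecasts nor worst cases, since valid results can also be misclassified. The shift example gives 24% missed at 94.5% valid, and depends on the assumed uniform counts and SD of 0.05.

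This should be corrected before analysis. It does not undermine data collection, because the pairs needed are already being recorded.

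**What to change.** 1. In 5.2, 14.1.1 and 15.1, state the primary comparison as the paired OLO-minus-laboratory neutrophil difference, with limits of agreement, in all tested Cohort 1 and 2 participants. Remove the restriction to valid results. Keeping both cohorts preserves the borderline-neutropenia half of the objective, which a classification in Cohort 1 alone would drop.
2. For Cohort 1, add a 2x2 classification at the ≤0.5 x10^9/L threshold the protocol cites, with sensitivity, specificity and Wilson 95% intervals.
3. Add a Table 7 indicator: the number of laboratory-neutropenic participants whom OLO classes as not neutropenic. Citing the existing management-change count would be an alternative. Either way, set the limit before OLO data are seen.
4. State whether the fidelity row is pooled or per cohort.

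**Cost.** Protocol wording and one extra table; no new patients, samples or data. The drawback is imprecision. With 16 neutropenic patients, perfect detection has a lower limit of 81%, and 15/16 gives 72% to 99%. With 14 (one third of the 43 planned valid Cohort 1 results, 43/3 = 14.3), perfect detection has a lower limit of 78%. The indicator can flag a problem but cannot establish accuracy.

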## 5.3 Secondary outcomes measure(s)

### ***Feasibility of recruiting patients and use of the OLO (Sight Diagnostics) system:***

- Proportion of those recruited from those consented and/or approached
- Proportion of recruited participants with a valid (as opposed to an invalid test result) from all recruited participants. A valid result is when the OLO system neutrophil result is  $\pm 0.2 \times 10^9/L$  of the laboratory gold standard result;
- Proportion of recruited participants returning the follow-up survey from all recruited participants;
- Number and type of OLO System (Sight Diagnostics) device flags and error codes raised during device operation for fingerprick versus venous blood sample to assess device accuracy;
- Number of re-takes of finger prick versus venous blood sample to assess device accuracy.
- Number of cases in which a discrepancy between the OLO System and gold standard would change the management of the patient, according to retrospective clinical review.
- Number of patients with valid OLO System test results for:
  - Haemoglobin – (validity  $\pm 0.7$  g/L)
  - Platelets – (validity  $\pm 15 \times 10^9/L$ )
  - Lymphocytes – (validity  $\pm 0.3 \times 10^9/L$ )

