## **4 Background**

### **4.1 Rationale for current trial**

Annually, in the UK >200,000 people receive chemotherapy as a part of their cancer treatment [1]. Chemotherapy kills rapidly dividing cells; however, this includes white blood cells (WBC): the body's defence against infections. Chemotherapy is administered for a set period of days over a number of cycles to ensure the optimal balance of recovery and clinical outcome, e.g. 6 cycles of 21 days. Patients receive treatment in the hospital and return home to cope with the side effects.

Following chemotherapy up to 10% of patients will experience complications that lead to a hospital admission. It is believed that a significant proportion of these admissions could be avoided by

integrating recent technological advances. Recent data suggests that patients with cancer desire a greater input to their cancer care [2], with greater control. This work is consistent with the evidence developed by Velindre University NHS Trust on patient values (see Figure 1) and clearly has the potential to provide patient enabling strategies based on a platform for:

- Choice;
- Control;
- Communication;
- Information;
- Independence;
- Highest quality of care

**Figure 4.** Evidence developed by Velindre University NHS Trust on patient values

All of which are aligned to the principle of co-production between patients, health care teams and government; included in Prudent Healthcare.

One of the most significant complications relating to chemotherapy administration is neutropenic sepsis. This condition is variably defined internationally but within the UK usually refers to a patient with a temperature  $\geq 38^{\circ}\text{C}$ , or clinical signs/symptoms of infection, and an absolute neutrophil count

$\leq 0.5 \times 10^9/L$  (3). Neutropenic sepsis carries the risk of prolonged hospital admission and untimely death, if not dealt with as a medical emergency. Timely medical attention with intravenous fluids and empirical antibiotics can improve outcomes and ultimately prevent death. Kumar et al have previously identified that for every hour of delay in antibiotic administration the risk of death increases by 7.8% (4).

A significant component of patient education delivered by cancer centre staff in the UK prior to and following the delivery of chemotherapy, relates to a need for the patient to inform the specialist medical team if they experience any fever of  $\geq 38^\circ\text{C}$  or if they feel unwell (5).

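### The flat ±0.2 ×10^9/L rule for a valid neutrophil result restricts the concordance analysis to pairs that already agree and can pass results on the wrong side of the 0.5 cut-off; the haemoglobin tolerance beside it is probably in the wrong unit

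*Protocol*

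**What the plan says.** Section 5.3 sets the rule for neutrophils: "A valid result is when the OLO system neutrophil result is" within ±0.2 ×10^9/L of the laboratory result. The same list gives flat tolerances for haemoglobin (±0.7 g/L), platelets (±15 ×10^9/L) and lymphocytes (±0.3 ×10^9/L). None has a percentage component, a count range or a rationale.

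Section 14.1.1 repeats the definition: "A valid OLO neutrophil result will be one which produces a test result which is within" ±0.2 ×10^9/L of the laboratory value. It evaluates concordance "across all patients with a valid output".

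Table 7 in section 15.1 makes the rule a progression criterion: "A valid test result is obtained from at least 90% of recruited participants who receive the OLO test".

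Two other statements fix the context. Section 4.1 describes neutropenic sepsis by fever or "clinical signs/symptoms of infection, and an absolute neutrophil count" of 0.5 ×10^9/L or less. Section 4.2.1 reports on audited admissions: "Two thirds did not have neutropenia, a proportion of whom may have avoided admission".

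**The concern.** The lay summary (section 3.2) asks whether the device can avert needless admissions and chemotherapy delays by excluding a low white cell count. That is a question about which side of a cut-off a patient falls. A single absolute band does not address it, and it means different things at different counts.

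- **Near 0.5** the band is wide relative to the cut-off, so a result can be valid and still classify the patient wrongly.
- **At ordinary counts** the band is a few percent of the value, so differences that change no decision can make a result invalid.
- **For concordance**, using validity as the entry condition removes the disagreements that the analysis is meant to measure.

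At stake are the reading of the 90% criterion, which signals whether modifications are needed before a larger study, and the accuracy evidence carried into that study. Separately, a haemoglobin tolerance in the wrong unit would make the device appear to fail on haemoglobin in most patients.

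**Working it through.** **1. The plan's own figure.** Section 14.1.1 gives 77.8% to 95.5% for 43 valid results of 48. Wilson interval: centre (43 + 1.921)/(48 + 3.842) = 0.8665; half-width 1.96 × √(43×5/48 + 0.960)/51.842 = 0.0882. The result is 77.8% to 95.5%, as stated. The Cohort 2 interval (22 of 24, 74.2% to 97.7%) also reproduces. The arithmetic is sound; the problem lies in what counts as valid.

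**2. Concordance among valid results.** If every difference lies within ±0.2, the mean difference must too, and the SD cannot exceed about 0.2. With zero bias the limits of agreement cannot exceed about 1.96 × 0.2 = ±0.39, however poorly the device performs in those left out.

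**3. At the cut-off of 0.5.** 0.2/0.5 = 40%. A neutropenic laboratory value L (at most 0.5) can have a valid OLO value above 0.5 whenever L + 0.2 > 0.5, that is, L above 0.3. Example: laboratory 0.45, OLO 0.65, difference 0.20, valid but reclassified. In the other direction, laboratory values from just above 0.5 up to 0.7 can have a valid OLO value of 0.5 or less.

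**4. At higher counts.** For an unbiased normal difference, 90% within ±0.2 needs SD ≤ 0.2/1.645 = 0.122. As a CV of the difference this is 24% at a count of 0.5, 6.1% at 2, 3.0% at 4 and 2.4% at 5. The share valid is 2Φ(0.2/(CV × count)) − 1. The protocol states no CV and no distribution of counts, so both are assumed ranges here:

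| CV of difference | count 0.5 | count 2 | count 4 | count 5 |
|---|---|---|---|---|
| 3% | 100% | 99.9% | 90% | 82% |
| 5% | 100% | 95% | 68% | 58% |
| 10% | 100% | 68% | 38% | 31% |

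Taking the audit split, with one third assumed at 0.3 and two thirds at a single higher count, the overall share valid at CV 3% / 5% / 10% is:
- higher count 2: 99.9% / 97% / 79%
- higher count 4: 94% / 79% / 59%
- higher count 5: 88% / 72% / 54%

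In Cohort 1, 90% of 48 is 43.2, so 44 valid results are needed if all 48 are tested. The binomial chance of 44 or more is 47% if the true share is 90%, and 2.5% if it is 80%.

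**5. Haemoglobin.** 0.7/80 = 0.88% and 0.7/150 = 0.47% (assumed range 80–150 g/L). For comparison, platelets ±15 is 15% to 6% at an assumed 100–250, and lymphocytes ±0.3 is 30% to 15% at an assumed 1–2. A band of ±7 g/L (0.7 g/dL) would be 8.8% to 4.7%, of the same order as the platelet tolerance. At an assumed 120 g/L and a CV of the difference of 1% / 2% / 3%, 44% / 23% / 15% fall within ±0.7 g/L, against about 100% / 99.6% / 95% within ±7 g/L.

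**The case against.** **Classification is not ignored.** Section 5.3 counts discrepancies that a retrospective clinical review judges would have changed management, and this can include pairs labelled valid. The cost outcomes in section 5.3 count positive and negative OLO results. So a reader who infers that no outcome looks at classification goes too far. What stands is narrower: none of these outcomes has a numerical cut-off, and none feeds the 90% criterion.

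**The trial can still answer its question.** The primary outcome (section 5.2) is the paired neutrophil counts, from which classification at any cut-off, bias and limits of agreement can be computed. The SAP is not at hand and may include them. It would be wrong to infer that the question is out of reach. However, a SAP that follows section 14.1.1 inherits its definition of valid and its restriction of the concordance set.

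**Valid output might mean only a technically successful run.** That reading is possible, and section 14.5 includes data from all participants. But the sentence that follows in section 14.1.1 defines valid by the ±0.2 band, so the text as written restricts the set.

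**Too strict is not shown.** It is tempting to conclude that a good device would fail. The documents do not support that: with a CV of 3%, or with non-neutropenic counts near 2, the criterion can be met. Section 14.2 warns of greater differences between finger-prick samples but gives no figure.

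**The consequences are limited.** The study is descriptive, and funding is not formally tied to Table 7. That holds, although a missed criterion is still said to call for modifications.

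**Conclusion.** The point holds in limited form. From the document alone: the neutrophil band is flat; it is 40% of the protocol's own cut-off; laboratory values from just above 0.3 up to 0.5 can be missed by a valid result; and concordance as worded is computed only on pairs already within ±0.2.

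The effect at higher counts is conditional. It becomes material once the CV of the difference exceeds about 3.0% at a count of 4 or 2.4% at a count of 5, and the protocol does not say whether it does.

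The haemoglobin unit slip is a strong inference from comparison with the sister tolerances. It is not proven, because the protocol gives no haemoglobin range or alternative unit, and haemoglobin carries no progression criterion.

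**What to change.** 1. In section 14.1.1, evaluate concordance on all participants with a numeric OLO result. Report OLO against laboratory classification at the protocol's 0.5 cut-off (for Cohort 2, at the site's existing decision value), with sensitivity, specificity and 95% CIs, plus bias and limits of agreement.
2. Report the ±0.2 proportion by count range, and do not let it alone stand for accuracy in the Table 7 criterion. If a percentage is added for higher counts, base it on the combined imprecision of both methods, including finger-prick sampling. Taking the larger of ±0.2 and a percentage can only widen the band and leaves the problem at 0.5 untouched, so at low counts also require agreement on the side of the cut-off.
3. Confirm the haemoglobin unit with the laboratory, and correct it if g/dL was meant.

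The cost is wording, a little more analysis of data already collected, and one imprecision figure from the laboratory lead if a percentage is used. Sensitivity will be imprecise: with one third of 48 neutropenic (16, assuming the audit split), even 16 of 16 detected gives a Wilson lower limit of 16/(16 + 3.84) = 81%. It should be presented as descriptive.
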